4.1.1 Treatment overview (Cohorts 1 & 2)

After being consented, patients will undergo baseline evaluations including clinical exam, complete blood count, blood chemistry, and thyroid function test. Baseline core or surgical biopsy and images with either CT scan or MRI scan will be obtained at screening. Blood collection for correlative analyses will be performed anytime after consent and prior to Nivolumab administration. Nivolumab 480mg will be administered intravenously on approximately Day -28 prior to planned surgery on Day 0 to Day +14 (14 day window as needed for scheduling surgery/logistics). An earlier surgery date is permissible if clinically indicated – see section 4.1.2 (salvage treatment).

Patients will undergo post-treatment images and specimen collection ideally within 7 days from planned surgery date, or as clinically indicated.

Post-operative adjuvant treatment with radiotherapy or chemoradiotherapy can be delivered, if clinically indicated at the discretion of treating physician following the standard of care. All subjects will

Johns Hopkins Protocol #: J1923

get follow up imaging about 3 months after completion of curative therapy (e.g. after adjuvant therapy) as per clinical routine.

After the initial post-treatment images, further imaging will be obtained as clinically indicated. In case of recurrence, a biopsy will be obtained and the specimen will be secured for future analyses if clinically feasible.

To explore oral and gut microbial correlates of response to neoadjuvant nivolumab, stool samples and oral rinses will be collected at baseline prior to infusion and then again prior to surgery. Subjects will also be asked to fill out a medical, antibiotic use and dietary questionnaire that will be used to assess whether antibiotic use or dietary patterns correlate with features of the oral and gut microbiome.

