1.2 Secondary Endpoints

- 1) Immune related pathologic response (irPRC)
→ irPRC criteria⁵¹ will be used – to assess resection specimen
- 2) Major pathologic response (MPR)
- 3) Progression free survival
Progression-free survival will be measured from the time of start of neoadjuvant nivolumab until radiologic or clinical progression or death.
- 4) Radiographic response rate
Response will be determined by RECIST version 1.1.

Exploratory

1. To determine changes in expression of selected immune markers and responses compared to baseline, in the blood, primary tumor tissue and draining lymph nodes from patients receiving neoadjuvant therapy; to determine changes in the quality and quantity of tumor infiltrating lymphocytes; and to compare findings in tumor and draining lymph nodes from treated patients, to findings in a parallel stage-matched cohort of untreated patients on a companion tissue collection protocol
2. To evaluate the potential effects of neoadjuvant therapy on normal head and neck mucosal tissue, by comparing tissues obtained on this study to those obtained from untreated patients undergoing tumor resection on a parallel tissue collection protocol.
- .
3. To compare immunologic markers and responses in HPV+ vs HPV(-) tumors. This includes

Johns Hopkins Protocol #: J1923

responses to HPV16 E6 and E7 antigens in patients with HPV+ cancers.

4. To explore features of the gut and oral microbiota of SCCHN patients before and after neoadjuvant nivolumab that may correlate with pathologic response.
5. To response to immunotherapy from pre- and on-treatment tissues in a histoculture model.
6. To assess recurrence-free survival in patients receiving preoperative therapy in this study.
7. To assess overall survival in high-risk patients with SCCHN receiving neoadjuvant therapy.
8. To study response to metabolic and or immunotherapy from pre- and on-treatment tissues in functional models (histocultures (slices/explants) and short term (< 4 weeks) in-vitro organoids) with in-vitro antibody testing.
9. To assess baseline immune and genomic tumor characteristics by performing multiplex immunofluorescence/immunochemistry (e.g., CD45, CD3, CD4, CD8, PDL1, etc.) and genetic sequencing (targeted and whole exome) on tissues slides/cryopreserved tissue blocks.

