4.10 Study calendar

| Procedure | Screening (Days -42 to -29) ^a | Day -28 | Pre- surgical evaluation (Days -7 to -1)** | Day 0 Surgery (up to day +14) | Post- surgical evaluation (Days 21 to 42) | Follow-up visits (Every 3-4 months for 1 yr; then every 6 months for 2nd yr.) ^{\$\$} | At the time of recurrence | Survival Follow-up (every 12 months) |
|--|--|------------|--|---|---|---|---------------------------------|---|
| Clinical Assessments | | | | | | | | |
| Physical Exam | X | X | X | | X | X | X | |
| Vital Signs | X | X | X | | X | X | X | |
| Performance status (ECOG) | X | X | X | | X | X | X | |
| Concomitant medicines | X | X | X | | X | X | X | |
| Toxicity assessments | X | X | X | | X | X | X | |
| Electrocardiogram (EKG) | X | | | | | | | |
| Laboratory Tests | | | | | | | | |
| CBC with diff | X | X**** | X | | X | X | X | |
| Chemistry including LFT | X | X**** | X | | X | X | X | |
| # IF abnormal LFTs draw: Hepatitis B/C serology | (X) [#] | | | | | | | |
| TSH | X | | | | X | X | | |
| Free T4 and T3 | X | | | | | | X | |
| PT/INR and PTT | X | | X | | | | X | |
| Pregnancy Tests (WOCBP only) | X | | X | | X | | X | |
| Treatment | | | | | | | | |
| Nivolumab | | X | | | | | | |
| CT neck/chest with IV contrast* | X | | X | | | (X) | (X) | |
| MRI neck with IV contrast, optional† | (X) | | (X) | | | (X) | (X) | |

| Procedure | Screening (Days -42 to -29) | Day -28 | Pre- surgical evaluation (Days -7 to -1) | Day 0 (and up to day +14) Surgery | Post- surgical evaluation (Days 21 to 42) | Follow-up visits (Every 3- 4 months for 1 yr; then every 6 months for 2nd yr.) ^{§§} | At the time of recurrence | Survival Follow-up (every 12 months) |
|---|-----------------------------------|----------------|--|---|---|---|---------------------------------|---|
| Correlative Blood/Tissue/Stool Studies | | | | | | | | |
| PBMCs, Serum, plasma (Blood collection 100 cc's) | | X ^b | | X | X | X | X | |
| Tumor biopsy/sample | X | | | X (resection specimen) | | | X | |
| Stool Sample | | X ^c | X | | X | X | X | |
| Oral Rinse ^d | | X | | | X | X ^d | X | |
| Medical & Dietary Questionnaire | | X | | | X | X | X | |
| Survival | | | | | | | | X |

- a. screening labs are permitted to be used for treatment if completed within three (+3) days of day -28
- b. Research blood permitted to be collected anytime after consent and prior to Nivolumab infusion (Days -42 to day -28)

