- c. Patients are to be provided with a stool collection kit during screening (days -42 to -29) and instructed to collect a stool sample within 48 hours of their scheduled infusion day (day -28).
- d. Oral rinse is considered an optional collection during the first and second year follow up visits.

*CT abdomen/pelvis can be added if there's a clinical indication. MRI may replace or supplement CT scans if clinically appropriate.

Ideally same imaging modality should be used for sequential imaging assessments.

** can be done on day of surgery also if necessary.

† MRI can be used at the treating physician's discretion; ideally same modality should be used throughout.

(X) as clinically indicated

*** Blood for correlates may be collected anytime after consent and prior to Nivolumab infusion.

Johns Hopkins Protocol #: J1923

***** Days -42 until/including Day -28

\$\$ F/u visits are allowable +/- 28 days or as clinically indicated

[See Appendix D](#) for Sociodemographic Characteristics Questionnaire

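### Section 4.1.1 requires a second oral rinse before surgery, but the study calendar schedules none between nivolumab and resection

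*Combined protocol and SAP*

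**What the plan says.** Section 4.1.1 (Treatment overview) sets one rule for both microbiome sample types: "stool samples and oral rinses will be collected at baseline prior to infusion and then again prior to surgery".

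The samples serve the fourth exploratory objective listed under Section 1.2: "To explore features of the gut and oral microbiota of SCCHN patients before and after neoadjuvant nivolumab that may correlate with pathologic response".

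The calendar in Section 4.10 gives stool and oral rinse separate rows. Stool is marked at Day -28, pre-surgical evaluation, post-surgical evaluation, follow-up and recurrence. The rinse is marked at Day -28, post-surgical evaluation, follow-up and recurrence. Its cells for the pre-surgical evaluation and for the day of surgery are blank.

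Two calendar footnotes could bear on this. Footnote d, the only one on the rinse, reads: "Oral rinse is considered an optional collection during the first and second year follow up visits". The double-asterisk footnote on the pre-surgical column says that its procedures "can be done on day of surgery also if necessary".

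**The concern.** The rinse before surgery is the only oral sample that could show the state of the oral microbiota after nivolumab but before the operation. Under the calendar, the first rinse after the drug is taken when the tumor has already been resected. Oral cavity and oropharynx are eligible primary sites (Section 3.1.1), so in some patients the operation is at or next to the sampled surface. Perioperative care comes in between as well, and possibly the start of adjuvant treatment (Section 4.6). A change between the Day -28 rinse and that later rinse could not be attributed to nivolumab. Once the patient has been operated on, the missed sample cannot be obtained.

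**Working it through.** The plan gives no figure to reproduce here. The check is a cell-by-cell reading of the calendar against the text, plus simple counts.

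**Step 1: is the calendar row read correctly?** The table has nine columns: the procedure name and eight visits. The stool and oral rinse rows each have nine cells. Footnote c concerns stool around the Day -28 infusion, and its mark sits under Day -28. Footnote d concerns the rinse at first- and second-year visits, and its mark sits under follow-up. The columns are therefore aligned, and the blank rinse cells fall under the pre-surgical evaluation and Day 0.

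**Step 2: scheduled samples by interval.**

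| Interval | Stool, Section 4.1.1 | Stool, calendar | Rinse, Section 4.1.1 | Rinse, calendar |
|---|---|---|---|---|
| Before infusion | 1 | 1 (Day -28) | 1 | 1 (Day -28) |
| After infusion, before resection | 1 | 1 (Days -7 to -1) | 1 | 0 |
| First sample after resection | not stated | Days 21 to 42 | not stated | Days 21 to 42 |

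Stool agrees in both places. The rinse differs by one sample, in the interval that matters.

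**Step 3: do the footnotes close the gap?** Footnote d relaxes the rinse at later follow-up visits and is silent on the pre-surgical visit. The double-asterisk footnote lets items in the pre-surgical column move to the day of surgery, but the rinse is not listed in that column. The Day -28 rinse cannot count as the second sample, because the text treats it as the baseline and asks for another.

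**Step 4: timing.** Counting from Day 0, with surgery on that day, a rinse at the pre-surgical visit falls 28 - 7 = 21 to 28 - 1 = 27 days after infusion, before resection. The calendar's next rinse falls 28 + 21 = 49 to 28 + 42 = 70 days after infusion, after resection.

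**Step 5: how many patients.** Section 4.1 plans 12 resected patients in each of two cohorts (12 + 12 = 24) and a total of 26. If f is the share of patients whose staff follow the calendar rather than the text, the number of missing samples is f × 24 to f × 26. The documents give no value for f:

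- f = 0: no samples missing.
- f = 0.5: 12 to 13 missing.
- f = 1: 24 to 26 missing.

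**The case against.** Several points on the other side have force.

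- **The text is operative.** Section 4.1.1 is part of the treatment plan and is worded as a requirement. Stool is already collected at the pre-surgical visit, so staff may well take the rinse with it. This stands, and it is why the loss is a range and not a fixed number.
- **The specified analysis does not need the second rinse.** The microbiota methods at the end of Section 11.2.2 compare responders with non-responders (Mann-Whitney tests, and UniFrac distances with PERMANOVA). No paired before-and-after test is named. This also stands: the Day -28 rinse supports that comparison. The objective is nevertheless worded as before and after the drug, and that part depends on the second sample.
- **The laboratory manual may settle it.** Section 11 refers to the manual for full details and lets it govern specific discrepancies where consistent with the protocol's intent. The manual is not among the documents, so it neither resolves nor confirms the gap.
- **A mark may have been lost when the table was read from the PDF.** This cannot be excluded for a single cell. But the row has its full cell count and its footnote mark is in the right place, so it is not the likelier explanation.

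A reader might also infer that the medical and dietary questionnaire must be added before surgery, so that antibiotic use between the paired samples is known. The documents do not support that as a required correction. Section 4.1.1 sets no time for the questionnaire, so there is no contradiction. The calendar also records concomitant medicines at both Day -28 and the pre-surgical evaluation, which largely covers antibiotic use in that interval.

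**Conclusion.** The inconsistency is real and confined to the oral rinse: one sample between infusion and resection in the text, none in the calendar. If the calendar is followed, between 0 and all of the roughly 24 to 26 patients would lack the oral sample after nivolumab and before resection. In those patients the on-treatment oral change would be confounded with surgery. This assumes that the calendar reads as extracted and that the laboratory manual does not already schedule the rinse.

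Two stronger readings are tempting. One is that every patient will lose the sample; that takes the calendar as overriding a mandatory sentence, which the documents nowhere say. The other is that the oral microbiome objective fails altogether. It does not, because the comparison of responders with non-responders on the baseline rinse remains possible. The stool pair is scheduled correctly, and the primary endpoint, the secondary endpoints and the stopping rules are untouched. The point affects the oral half of one exploratory objective. It deserves correction because the loss cannot be reversed and the remedy costs almost nothing.

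**What to change.** Add an oral rinse mark to the pre-surgical evaluation column (Days -7 to -1) of the calendar in Section 4.10, so that it matches Section 4.1.1 and the stool row. The double-asterisk footnote would then also allow the rinse on the day of surgery. Check that the laboratory manual agrees.

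The cost is one calendar entry. The rinse is non-invasive, the text already requires it, and the visit already takes place with a stool collection. No change to the questionnaire schedule is needed.

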4.1.2 Early salvage treatment options: salvage surgery, salvage chemotherapy

In patients with clinically worsening disease, or concern that resectability may be at risk, or due to extenuating scheduling circumstances, an earlier surgery date can be approved in consultation with the treating surgeon, medical oncologist, and study team.

Alternatively, neoadjuvant chemotherapy can be given in patients with clinically worsening disease, or concern that resectability may be at risk after approval and review by the treating surgeon, and medical oncologist, and study team.

Such 'salvage' patients will continue on study, unless deemed non-evaluable for other reasons.

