4. TREATMENT PLAN

4.1 Overall Study Design and Toxicity Assessment

The study will accrue to 2 cohorts, each of which consists of 12 patients who undergo surgical resection. Total of 26 patients will be accrued to the study. Patients who do not undergo surgery for reasons unrelated to toxicity of the study treatment will be replaced and will not count toward the accrual goal of 12 surgically resected patients in each cohort. If enrollment on 1 cohort is significantly faster, the lesser enrolling cohort number of patients may be decreased in favor of the better enrolling cohort to keep the total number of evaluable patients at 26 pts (also see statistical section).

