4.8 Discontinuation, withdrawal and replacement of subjects

All patients who receive at least one dose of study treatment (including those who do not undergo surgical resection of their tumor) will be included in the overall evaluation of safety (intention-to-treat analysis). All reasons for discontinuation of therapy should be documented clearly in the medical record. If a subject discontinues or withdraws from the study, every attempt will be made to obtain an off-study blood collection if the subject is able and willing to do so.

Subjects who do not undergo surgical resection of their tumor, while evaluable for safety and feasibility, will not be evaluable for the key secondary endpoint of pathologic response. Subjects who sign a consent form but do not initiate protocol treatment for any reason (e.g., subjects who are screen failures), and patients who do not undergo surgical resection (for reasons unrelated to the study drug or toxicity) will be replaced and will not count towards our accrual goal.

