9. MEASUREMENT OF EFFECT

9.1 Pathologic evaluation

Assessment of immune related pathologic response (irPRC) is the first secondary endpoint of the study as defined by Stein et al.⁵¹

Diagnostic pathology specimen will be collected and processed following the treating institution's standard operating procedures and will be evaluated by a head and neck pathologist.

Major pathologic response (mPR) will also be assessed and is defined as $\leq 10\%$ residual tumor

tissue on all reviewed specimens of each subject.

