9.2.1 Definitions

Evaluable for toxicity. All patients will be evaluable for toxicity from the time of their first treatment on protocol.

Evaluable for objective response. All patients will be evaluable for objective response after completing the first treatment on protocol, as long as they get radiographic evaluation with either CT scans or MRI scans on the specified timeframe.

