10.1.2 Endpoints

Primary Endpoint

Safety and feasibility of neoadjuvant nivolumab administration in patients with newly diagnosed head and neck cancer and those with locoregional recurrence or oligometastatic disease undergoing surgical resection, measured by 1) frequency of drug-related adverse events occurring up to 100 days after the last dose of nivolumab or 30 days after surgery (whichever is longer), and 2) successful completion of preoperative treatment and proceeding to surgery without any extended treatment-related delays greater than 28 days from the preplanned day 0 (or 14 days from day +14).

Secondary Endpoints

Immune related pathologic response (irPRC)
As defined by Stein et al (CCR 2019)⁵¹

Major pathologic response rate

Defined as $\leq 10\%$ residual tumor in the resection specimen after neoadjuvant nivolumab

Progression-free survival

Progression-free survival will be measured from the time of initiation of nivolumab until radiologic or clinical progression or death.

Radiographic response rate

Response will be determined by RECIST version 1.1.

Laboratory correlates of immune activity and response

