10.3 Analysis of secondary endpoints

We will obtain pathology reports from all surgical specimens and tabulate the data to obtain rate of pathologic CR. Descriptive reports of pathology findings for each cohort will also be reported. We will estimate progression-free survival probabilities using the Kaplan-Meier method. Progression-free survival is defined as the time from the first dose of nivolumab until progression or death from any cause. Toxicities will be categorized by frequency and type, and reported in tabular form for each cohort and all subjects on the trial. All patients will be evaluable for toxicity from the time of their first treatment with any study therapy.

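### The written rules allow a pathologic response found after salvage chemotherapy to enter the nivolumab response rate, and no rule excludes or flags it

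*Combined protocol and SAP*

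**What the plan says.** Section 4.1.2 gives two salvage routes before the planned operation: earlier surgery or chemotherapy. On the second it says that "neoadjuvant chemotherapy can be given in patients with clinically worsening disease", or where resectability is feared to be at risk, after review by the surgeon, the medical oncologist and the study team. It then says that such "patients will continue on study, unless deemed non-evaluable for other reasons".

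Four other places govern the pathologic endpoint:

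- Section 4.8: subjects who are not resected "will not be evaluable for the key secondary endpoint of pathologic response". No other ground for non-evaluability is given for this endpoint.
- Section 9.1: MPR is at most 10% residual tumor "tissue on all reviewed specimens of each subject".
- Section 10.1.2: MPR is at most 10% "residual tumor in the resection specimen after neoadjuvant nivolumab". The immune-related pathologic response (irPRC) is listed before it and is defined only by a cited publication.
- Section 10.3: "We will obtain pathology reports from all surgical specimens and tabulate the data to obtain rate of pathologic CR". It names no rate for MPR or irPRC response and states no denominator or interval for either.

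Section 4.1 sets an "accrual goal of 12 surgically resected patients in each cohort". Sections 4.1 and 10.2 also give a total of 26.

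**The concern.** One reason for giving the chemotherapy is that the disease got worse after nivolumab. If the resected specimen then shows little residual tumor, the rules as they stand let that patient be reported as a pathologic responder under a heading that speaks of nivolumab. Nothing in the table would tell the reader that chemotherapy came in between.

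Section 4.8 calls pathologic response the key secondary endpoint. Section 2.3.1 says it is unclear what response to expect in previously treated patients, so the Cohort 2 rate would be read as new information. The same patients could also enter the correlative work. Section 1.2 seeks microbiome features that go with pathologic response, and Section 11.2.2 compares responders with non-responders without defining a responder.

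**Working it through.** **Step 1: follow one patient through the rules.** Take a patient who receives nivolumab, worsens, receives chemotherapy under Section 4.1.2, and is resected with at most 10% residual tumor.

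| Question | Rule | Result |
|---|---|---|
| Still on study? | 4.1.2: yes, unless non-evaluable for another reason | Salvage alone does not remove the patient |
| Evaluable for pathologic response? | 4.8: only lack of resection makes a patient non-evaluable | Evaluable |
| Meets the MPR definition? | 9.1 and 10.1.2: residual tumor; neither requires nivolumab to be the only preoperative therapy | Yes |
| Specimen in the table? | 10.3: all surgical specimens | Yes |
| Any rule that excludes, flags or lists it apart? | None found | No |

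Section 4.9 lists significant preoperative progression as a reason to discontinue protocol treatment, but attaches no consequence for this endpoint.

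**Step 2: reproduce the plan's own figures.** The plan gives no figure for pathologic response. Its exact intervals for 12 patients are in Section 10.2. With x events in n patients, the Clopper-Pearson limits are the 2.5% quantile of Beta(x, n−x+1) and the 97.5% quantile of Beta(x+1, n−x). All five printed intervals reproduce: 0/12 (0–26.5%), 1/12 (0.2–38.5%), 2/12 (2.1–48.4%), 12/12 (73.5–100%) and 11/12 (61.5–99.8%).

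**Step 3: shift per credited response.** Crediting one further response changes the rate by (x+1)/n − x/n = 1/n.

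- One cohort, n = 12: 1/12 = 8.3 points.
- Two cohorts of 12 resected patients, n = 24: 1/24 = 4.2 points.
- Total of 26, if all are resected: 1/26 = 3.8 points.

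Both 24 and 26 are shown because Sections 4.1 and 10.2 contain both figures.

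**Step 4: illustration with assumed counts.** In each row, one MPR occurs after salvage chemotherapy and the rest after nivolumab only.

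| Resected patients | Credited, as the rules allow | Kept in denominator, not credited |
|---|---|---|
| 12 | 3/12 = 25.0% (5.5–57.2) | 2/12 = 16.7% (2.1–48.4) |
| 24 | 4/24 = 16.7% (4.7–37.4) | 3/24 = 12.5% (2.7–32.4) |
| 26 | 6/26 = 23.1% (9.0–43.6) | 5/26 = 19.2% (6.6–39.4) |

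In the cohort of 12, the rate in patients who had nivolumab only is 2/11 = 18.2% (2.3–51.8).

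**Step 5: how likely is it?** The documents give neither a salvage frequency nor a response rate after salvage. Let s be the share of patients resected after salvage chemotherapy and r the MPR rate among them, both assumed. The chance of at least one such responder is 1 − (1 − s·r)^n.

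| s, r (assumed) | n = 12 | n = 26 |
|---|---|---|
| 2%, 10% | 2.4% | 5.1% |
| 5%, 20% | 11.4% | 23.0% |
| 10%, 40% | 38.7% | 65.4% |

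The range is wide because the inputs are unknown.

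**The case against.** The strongest reply is that this reads a rule into silence. Section 4.1.2 speaks of staying on study, not of how a specimen is scored, and Section 10.3 does not say that its rate belongs to nivolumab alone. It is true that no sentence credits such a response. But the gap is more than silence. Staying on study, a single ground for non-evaluability, a definition based on residual tumor and a table of all specimens lead to inclusion when each is followed. A handling rule chosen once the pathology is known would be open to bias.

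A second reply is that the effect is small and hypothetical. The shift of 8.3 points sits inside intervals 46.3 points (2/12) and 51.7 points (3/12) wide, and the event may never occur. That stands. It limits the weight of the point but does not remove the gap.

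A third reply is that withholding credit can also mislead. Chemotherapy may be given on concern about resectability alone, and a true nivolumab effect in that patient would then be lost. That also stands. It is why the rate in nivolumab-only patients and a listing should accompany the main rate.

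A reader might also infer that irPRC scoring certainly credits these specimens. The documents do not settle that, because irPRC is defined by a publication they do not reproduce. The reasoning from definitions applies to MPR; for irPRC, the documents show only that no rule excludes such specimens.

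**Conclusion.** The point holds as an inference from Sections 4.1.2, 4.8, 9.1, 10.1.2 and 10.3 read together. Relative to not crediting it, each response after salvage chemotherapy raises the reported rate by 8.3 points in a cohort of 12, 4.2 in 24 and 3.8 in 26. The number of such patients is not given, and with none the effect is zero.

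A reader might infer more than the documents support:

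- That the trial's inference is compromised. Pathologic response is descriptive and has no threshold, so no type I error or power is affected. The primary safety and feasibility populations are defined separately in Section 10.2.
- That the reported rate will be too high. The upward direction holds for each credited response against the alternative of not crediting it. Whether any will occur is unknown, and the chances in Step 5 are assumptions.

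The point is worth acting on because the endpoint is called key, one patient moves a cohort rate visibly, and the remedy is cheap.

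**What to change.** Amend Section 10.3; this concerns analysis only and leaves the salvage provisions as they are.

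1. Report MPR and irPRC response, the listed endpoints, alongside pathologic CR. Give each by cohort with an exact 95% CI, in resected patients.
2. In the main rate, keep patients who received other systemic anticancer therapy between nivolumab and surgery in the denominator, but do not credit them as nivolumab responders.
3. Beside it, show the rate in resected patients who received nivolumab only.
4. List the salvage-chemotherapy patients with their pathology, and flag them in responder versus non-responder correlative comparisons.

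The cost is a few lines of text, one derived flag and one extra rate per endpoint. The data should be to hand: the study calendar in Section 4.10 already records concomitant medicines, and Section 4.1.2 already requires study-team approval of each salvage chemotherapy case. The downside is that the main rate may be slightly less favourable and may miss a true nivolumab effect in a flagged patient; the listing makes that visible.
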